## 6 STUDY DESIGN

[figure not shown]
### 6.1 Overview of the study design and dose regimen

This is a Phase III, multi-center, randomized, 48 weeks, double-blind, parallel-group, placebo-controlled study to evaluate efficacy and safety of CER-001 on ApoA-1 and vessel wall area in patients with genetically defined familial primary hypoalphalipoproteinemia and receiving background optimized lipid therapy.

Double-blind treatment phase: After obtaining written informed consent and provided the patient fulfills the selection criteria as defined in *section 7*, he/she will be randomized to receive twenty-nine doses of CER-001 or placebo, weekly during the first 8 weeks (9 doses) and then every two weeks during the following 40 weeks (20 doses). Dosing visits will have a window of +/- 2 days around the strict weekly or biweekly date.

Open-labeled treatment phase: After obtaining written informed consent, patient will receive twelve doses of CER-001, one every two weeks during 24 weeks following the last dose administered during double-blind treatment period. Dosing visits will have a window of +/- 2 days around the strict biweekly date.

Patients will have a safety follow-up visit at least 30 days after the last dose administered.

**Figure 1. Schematic study design.**

### 6.1.1 Study periods

The study duration can be up to 68 to 92 weeks in total:

- Screening period: up to 16 weeks (+/- 7 days)
- Treatment period: the overall treatment period is 48 weeks (+/- 7 days) including an induction treatment phase of 8 weeks, followed by a 16 week maintenance treatment phase and a 24 week extension treatment phase.
- Safety follow-up period: 4 weeks (+/- 7 days) after the end of treatment OR
- Safety extension follow-up: 24 weeks (+/- 7 days) AND Safety follow-up period: 4 weeks (+/- 7 days) after the end of treatment

### 6.1.2 Rationale for the study design

In the present study, CER-001 will be evaluated at 8 mg/kg dose as its potential to induce regression of carotid atherosclerosis in patients with FPNA. As already described, both MODE (18) and SAMBA (17) studies have proven this dose as efficacious especially in the population addressed in this study (See section 3.3.2. Clinical Findings for CER-001).

Both previous trials mentioned above were designed to address the efficacy of CER-001 at 6 months. Indeed, even though infusion of CER-001 was leading to early positive effect on carotid atherosclerotic plaque burden as detected by a significant reduction of the mean carotid vessel wall area after 1 month treatment (17), it is of main interest to measure the longer lasting effect of the study drug and maintenance of its positive treatment outcome on atherosclerotic plaques. Therefore this study has been designed to confirm the previous clinical evaluation. Moreover, the 24 week extension treatment period (See *Figure 1*) will allow to assess even further beneficial effect of 8 mg/kg dose of CER-001 as well as better evaluating the safety profile of the study drug by collecting safety data from the patients with FPHA exposed to CER-001 for 48 weeks. A final safety visit will occur at week 52.

## **6.2 Dose and Dose Regimen Selection**

Overall CER-001 has shown its potential benefit in various patient populations. Patients receiving 8 mg/kg dose of CER-001 in the MODE study (18) indicate that six months biweekly infusion of CER-001 at 8 mg/kg is beneficial in regressing carotid plaque in patients with Homozygous FH who were receiving optimized LDL-lowering therapy.

Moreover and remarkably CER-001 8 mg/kg transiently restored the population of HDL particles in patients with FPHA in the SAMBA study (17). Cholesterol mobilization was consequently increased along with fecal sterol excretion. CER-001 decreased inflammation in the carotid arteries. CER-001 treatment resulted in plaque regression in the carotids and aorta after 4 weeks of induction therapy and the effect was maintained over six months.

The present study will evaluate the efficacy of 8 mg/kg dose of CER-001 as assessed by 3T-MRI aiming to confirm and validate the benefit on atherosclerosis previously observed in patients with FPHA.

The dose and the dose regimen of the TANGO study are based on the previous positive SAMBA study that included an induction and a maintenance phase.

## **6.3 End of the study**

The study will end when the last randomized patient completes the last assessment 4 weeks after the end of the treatment period.

## **6.4 Number of patients and assignment to treatment group**

A total of 30 patients are planned to be randomized. Treatment groups include 8 mg/kg dose of CER-001 and placebo. Patients will be recruited over a planned recruitment period of 9 months. FPHA is a rare disease explaining the small number considered for this clinical study. The number of patients may slightly increase depending on the ability to find patients with FPHA and a clinical profile matching with the inclusion and exclusion criteria as defined in *Section 7*.

Considering the profile of patients targeted in this study, twice more patients will be randomized into the active 8 mg/kg dose of CER-001 group as compared to those patients who will be randomized into the placebo group - randomization in a 2:1 ratio.

## **6.5 Centers & countries**

Approximately 15 sites from Europe, Canada, United States of America, Brazil and Israel will be involved in this study based on availability of identified patients with this rare disease.

## **6.6 Safety extension protocol**

Patients having completed their last infusion 48 weeks after the first one will be offered to continue in the study for 6 months for safety follow-up.

All patients who accept to continue will be treated with CER-001 8mg/kg whatever the randomization arm. A total of 12 infusions will be administered bi-weekly until week 72. A 3T-MRI scan assessing the carotid and femoral artery will be optimally performed at this visit. A final safety visit will occur at week 76, 4 weeks after the last infusion.

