### **8.3 Clinical Assessments and Procedures during the Double-blind Treatment Period**

Patients will visit the clinic each week for the first 8 weeks and every 2 weeks thereafter until the end of the treatment period (week 48) as described in Appendix A. At each visit, the patient will receive an infusion and will be checked for:

- Adverse events
- Previous and concomitant medications

Complete assessments as described for visit 2 (see *Section 8.2* above) will be performed 4 weeks and 8 weeks after randomization (at visit 6 and visit 10). Thereafter, patients will have complete assessments every 8 weeks until the end of the week 48 treatment period (at week 16, 24, 32, 40 and 48). Unless otherwise specified, blood and urine specimens will be collected prior to study drug dosing.

Markers of inflammation, oxidation, lipid metabolism and CV risk (See *Section 8.10*) will be assessed at baseline, week 8, week 24 and week 48 (end of treatment).

HbA1c assessment will be performed only at baseline (See *Appendix A*).

Anti-ApoA-1 antibody assessment will be performed at week 8, week 24 and week 48 (end of treatment).

Blood samples will be collected for biomarkers assessments at week 24.

A blood sample will also be drawn two hours after initiation of the infusion to assess the PK, at week 24.

Follow-up 3T-MRI will be done at the end of the induction treatment phase (week 8), week 24 and at the end of the overall week 48 treatment period.

Follow-up FDG-PET/CT will be performed only once 24 weeks after randomization.

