### For patients treated until week 72:

A safety follow-up for the patients will be conducted by phone 4 weeks (+/- 7 days) after the final dose of study medication and will include:

- Previous and concomitant treatments
- Adverse Events

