#### **8.8 Assessment of Safety**

During double-blind treatment period, all patients who receive at least one dose of study medication and have a subsequent safety evaluation will be included in the safety analyses.

Safety assessments will include:

- Physical exam
- Vital signs assessments
- Electrocardiogram (ECG) assessments

- Laboratory tests
- Adverse events (AEs)
- Metabolic parameters
- Urinalysis
- Anti-ApoA-1 antibody

During open-labeled treatment period, all patients who receive at least one dose of CER-001 and have a subsequent safety evaluation will be included in the safety analyses.

Safety assessments will include Adverse Events (AEs).

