### **8.8.4 Clinical Laboratory Tests**

Laboratory tests should be measured at the screening visit, randomization, at week 4, week 8 and every 8 weeks thereafter until the end of treatment. Additionally, laboratory tests will be done at the follow-up visit. Any blood sample collected according to the Schedule of Assessments (Appendix A) may be analyzed for any of the tests outlined in the protocol. This may also include, but is not limited to, investigation of unexpected results and incurred sample reanalysis.

Clinical laboratory safety testing during the screening and treatment periods will be performed by a central laboratory. Collection kits, shipment instructions, and a detailed clinical laboratory manual will be provided to the study sites. Investigators are required to review the labs upon receipt and make a determination of clinical significance for labs outside of the normal range. All laboratory reports must be reviewed, signed and dated by a medically trained investigator. Clinical laboratory safety testing will consist of the following panels of laboratory tests. The details of which tests are performed at each visit can be found in Appendix A.

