## **URINALYSIS**

Microalbuminuria  
Specific Gravity  
pH  
Glucose  
Total Protein  
Ketones  
Total Bilirubin  
WBC  
RBC  
Casts

The results of all laboratory tests required by the protocol will be documented and will be transferred to the study database via 21 CFR 11 compliant methodology. All clinically important abnormal laboratory tests occurring during the study will be repeated at appropriate intervals until they return either to baseline or to a level deemed acceptable by the Investigator and the Medical Monitor, or until a diagnosis that explains them is made.

The criteria for determining whether an abnormal objective test finding should be reported as an adverse event are described in *section 11.1*.

A serum pregnancy test will be done at screening visit only. Urinary pregnancy test will be used during the course of the study.

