**Hepatic Stopping Criteria:**

In the case of Liver Function Test elevation  $> 3 \times \text{ULN}$ , additional workup may be required within 24 hours of the event by the investigator in close consultation with the Sponsor according to established protocols. This is to rule out possible cases of Hy's law.

Patients should have dosing withheld if the most recently obtained serum ALT or AST exceeds five times the upper limit of normal. If the most recently obtained serum ALT or AST elevation is greater than the upper limit of normal but less than five times the upper limit of normal, the patients may receive their next dose, which may be reduced in consultation with the Sponsor (see *Section 10.3* for more details).

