## APPENDIX B: Schedule of Assessments in open-labeled treatment phase

	V31 to V41 W50 to W70	V42 W72	V43 FU W76
Informed Consent	X		
Selection criteria (Inclusion/Exclusion)			
Medical history			
Demography			
12-Lead ECG			
Height			
Weight			
Pregnancy Test			
Physical Exam			
Vital Signs			
Blood Pressure (BP) & Heart Rate (HR) assessment			
Hematology/coagulation			
Serum Chemistry			
Urinalysis			
Adverse Events	X	X	X
Previous and concomitant medications	X	X	X
FSH			
Counseling on heart healthy diet and lifestyle			
Genotyping			
Markers of inflammation, oxidation and CV risk			
Biomarkers sample			
HbA1c			
Fasting blood glucose			
Lipid & Lipoprotein Profile			
Anti-ApoA1 antibody			
Creatinine and/or BUN testing to determine GFR			
Cellular Cholesterol Efflux			
Study drug infusion	X	X	
Pharmacokinetics (PK)			
3TMRI (MVWA)		X	
 FDG-PET/CT			

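### Former placebo patients start CER-001 at week 50, but no serum chemistry is scheduled from week 50 to week 76, so the hepatic dosing rules in Protocol 11.7 have no scheduled value from open-label dosing

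*Protocol*

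**What the plan says.** **Treatment.** Protocol 6.6 offers patients who complete the W48 infusion a further six months: "All patients who accept to continue will be treated with CER-001 8mg/kg whatever the randomization arm". There are 12 infusions, one every two weeks, the last at W72. Section 6.4 plans 30 patients randomised 2:1.

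**Monitoring in the extension.**
- 8.4 lists adverse events and medications at each visit, and an MRI at W72.
- 8.8 says of the open-label period: "Safety assessments will include Adverse Events (AEs".
- In "APPENDIX B: Schedule of Assessments in open-labeled treatment phase", the serum chemistry and creatinine/BUN rows are empty for W50 to W70, W72 and W76. The adverse event, medication, infusion and MRI rows carry marks.
- 8.5, for patients treated to W72: "A safety follow-up for the patients will be conducted by phone 4 weeks" after the final dose, covering medications and adverse events.
- SAP 7.5.3 ends biochemistry at W48.

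**Dosing rules.** Section 11.7 states: "Patients should have dosing withheld if the most recently obtained serum ALT or AST exceeds five times the upper limit of normal". It also calls for discontinuation on ALT or AST above 8 times the upper limit of normal (ULN), on ALT or AST above 5 times ULN for more than two weeks, or on a Hy's law case. For the kidney it asks for special attention to creatinine raised at two or three consecutive tests after dosing, or to low creatinine clearance. Nothing in 11.7 confines these rules to the double-blind phase.

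**Timing of the last sample.** In the double-blind phase, unless otherwise specified, "blood and urine specimens will be collected prior to study drug dosing" (8.3).

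**The concern.** A laboratory-based dosing rule works only if someone takes the sample. In the extension the hepatic rules stay in force, but nothing on the schedule supplies them with a value. This matters most for former placebo patients. Their W48 chemistry is a baseline for CER-001, not a safety reading on it, and it would remain the most recent scheduled result through 24 weeks of first exposure. A symptomless rise in ALT or AST in such a patient would not be found on schedule, and infusions could continue where 11.7 directs that they be withheld or stopped. The opening of 11.7 names liver and kidney as possible target organs on the basis of toxicology studies, so these are the tests the protocol itself treats as relevant to dosing.

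**Working it through.** **Inputs.** N = 30 and 2:1 allocation (6.4); 12 open-label infusions to W72 (6.6); visit weeks W50 to W72 (Appendix B); double-blind chemistry at W0, 4, 8, 16, 24, 32, 40 and 48 (Appendix A); 20% discontinuation (12.4).

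**The plan's own counts.**
- Double-blind infusions: 9 weekly (W0 to W8) + [(48 − 10)/2 + 1 = 20] = 29, as stated.
- Open-label infusions: (72 − 50)/2 + 1 = 12, as stated.

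**Sampling density in the double-blind phase.** Samples precede the dose, so count the infusions from one sample up to the next: [0,4), [4,8), [8,16), [16,24), [24,32), [32,40) and [40,48) each hold 4. The W48 infusion brings the total to 7 × 4 + 1 = 29.

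**Sampling density in the extension.** 12 infusions, 0 scheduled samples.

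| Quantity | Calculation | Result |
|---|---|---|
| Newly exposed patients | 30 × 1/3 | up to 10 |
| Same, with 20% discontinuation | 10 × 0.8 | 8 |
| Infusions given to former placebo patients after CER-001 exposure has begun (W52 to W72) | (72 − 52)/2 + 1 | 11 of 12 |
| Age of the W48 value over those infusions | 52 − 48 to 72 − 48 | 4 to 24 weeks |
| Former CER-001 arm: infusions at or beyond the next 8-weekly point (W56 to W72) | (72 − 56)/2 + 1 | 9 of 12 |

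**Does other text fill the gap?**
- Section 8.8.4 continues laboratory tests to the end of treatment, which read alone could reach W72. But it adds: "The details of which tests are performed at each visit can be found in Appendix A". Appendix A is the double-blind schedule, and the text specific to the extension schedules no tests.
- The chemistry four weeks after W48 is listed in 8.5 for patients treated until W48. Section 6.1.1 presents that follow-up and the extension as alternatives. Footnote 14 of Appendix A mentions all patients but ties the visit to the last dose, which is W72 for those who continue.
- Section 8.8.4 also says: "All clinically important abnormal laboratory tests occurring during the study will be repeated at appropriate intervals until they return either to baseline" or an acceptable level. That follows up abnormalities already found. It does not prompt a test in a symptomless patient whose W48 result was normal.

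**With samples at W54, W58 and W66.** Open-label infusions fall as [50,54) = 2, [54,58) = 2, [58,66) = 4 and W66 to W72 = 4; total 12. No interval exceeds 4, as in the double-blind phase. Former placebo patients would have three values after exposure, enough for the two- and three-value creatinine criteria.

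**The case against.** **The extension is deliberately light.** Sections 8.4, 8.5, 8.8 and 8.14.3 and Appendix B are consistent, and 8.14.3 defines 72-week safety through adverse events. This stands. A reader might infer that the 72-week safety objective cannot be met; the documents do not support that, because the objective is defined without laboratory data.

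**The hepatic rule still has an input.** It uses the latest available ALT or AST, so the W48 value counts, and at W50 it is a proper baseline. Patients are seen every two weeks and can be tested for cause. This also stands, so it would be wrong to say the rule cannot operate. What remains is that no scheduled value comes from open-label dosing.

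**The kidney criteria do not stop dosing.** A reader might infer that 11.7 would withhold or stop CER-001 on creatinine. It would not: it asks for attention and lets the investigator choose to discontinue if the drug is thought responsible. The dosing consequence is limited to the hepatic rules.

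**The human data are reassuring.** Section 11.7 reports no significant laboratory abnormalities in humans to date. Section 11.6 says liver enzyme rises were not seen above the placebo rate. Section 5 cites more than 400 exposed patients, 122 of them at 12 mg/kg. Section 3.3.2 reports good tolerability at 8 mg/kg every two weeks for up to 12 months in one study, and unremarkable chemistry in patients with this disease in another. All of this lowers the stakes and keeps the point well short of a major safety defect.

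**A visit at W76 might include laboratory tests.** Section 6.6 calls W76 a visit, while 8.5 makes it a phone contact. The more specific text in 8.5 and Appendix B probably governs, but the two should agree.

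**Conclusion.** The gap is real: 12 open-label infusions with no scheduled ALT, AST, bilirubin or creatinine, against one chemistry sample per 4 infusions in the double-blind phase. For up to 10 former placebo patients, 11 of the 12 infusions follow first CER-001 exposure while the only scheduled chemistry predates it. The directive hepatic rules are affected; the discretionary renal criteria likewise lack the serial values they refer to.

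The figure of 10 assumes N = 30, although 6.4 allows a slight increase, and that every former placebo patient continues. The documents do not give the expected uptake. The reading also assumes that the text specific to the extension prevails over the general laboratory paragraph in 8.8.4. If 8.8.4 was meant to apply, the protocol contradicts itself and still needs correcting.

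Severity is minor to moderate. The risk is probably low, and the case for change rests mainly on its low cost.

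**What to change.** **Protocol 8.4, 8.8 and Appendix B.** Add pre-infusion ALT, AST, bilirubin and creatinine at W54, W58 and W66, which are existing infusion visits, and state that 11.7 applies in the extension. Use one schedule for all continuing patients. Testing only former placebo patients would reveal their double-blind arm, whereas 9.10 and 9.11 keep sites and sponsor blinded until the database is locked after the last patient's final visit.

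**W72, optional.** A sample here is an end-of-treatment safety check, not a dosing input. It goes to a central laboratory, so the result would normally follow the last infusion, and no later dose remains to be guided.

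**Alignment.** Make 6.6 and 8.5 agree on whether W76 is a visit or a phone contact. Add the new time points to SAP 7.5.3 as listings.

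**Cost.** Three samples per continuing patient: at most 3 × 30 = 90, or 3 × 24 = 72 if only 24 continue. With W72, 4 × 30 = 120 or 4 × 24 = 96. Add collection kits, a protocol amendment with ethics review across about 15 sites, and a short SAP edit. No extra visits or staff are needed.

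**Limits.** Samples taken about 14 days after the previous dose may miss short-lived rises; section 3.3.1 reports that high-dose animal changes generally reversed within 24 to 48 hours. Without W72, the last four infusions (W66 to W72) have no later scheduled test; with it, only the W72 infusion lacks one.

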# **7 STUDY POPULATION**

## **7.1 Population to be studied**

Patients with  $\text{ApoA-1} \leq 110 \text{ mg/dL}$  and  $\text{HDL} \leq 35 \text{ mg/dL}$  with suspected homozygous or heterozygous mutation in the *ABCA1*, and/or *ApoA-1* genes confirmed by genetic testing and background of symptomatic or asymptomatic cardiovascular disease, will be eligible for this study.

Patients, who fulfill all inclusion/exclusion criteria, including confirmation of a genetic defect, may be enrolled in the study.

## **7.2 Inclusion criteria**

**A patient may be randomized if the answer to all of the following statements is “yes”.**

### **Demographic**

1. Male and female patients, aged 18 and above
2. Female patients who are not either surgically sterilized (e.g., tubal ligation or removal of ovaries or uterus) or post-menopausal (no spontaneous menstrual periods for at least one year) must agree to use one of the following forms of contraception from screening until 90 days after the completion of the study medication: (1) systemic hormonal treatment (2) an IUD which was implanted at least 2 months prior to screening or (3) "double-barrier" contraception (condom, diaphragm and spermicide are each considered a barrier), or (4) agree to remain sexually abstinent during the entire study period (when contraception is not acceptable for cultural or religious beliefs)

**Procedural**

3. Sign written informed consent after the scope and nature of the investigation have been explained to them before screening evaluations and willing to comply with the study restrictions
4. Are fluent in the language of the investigator, study staff (including raters), and the informed consent

**Clinical**

5. Diagnosis of genetically confirmed HDL-c deficiency due to defects in genes coding for e.g. ABCA1 and/or ApoA-1
6. IF the subject is on lipid-lowering therapy or NEEDS to be treated with lipid-lowering therapy then the subject must be on a stable dose at least 6 weeks prior to the baseline procedures.
7. Background symptomatic or asymptomatic cardiovascular disease should be present as such:
  - For symptomatic cardiovascular disease: i) history of cardio or cerebrovascular events, ii) diagnosed coronary artery disease (CAD), iii) diagnosed carotid or peripheral stenosis, iv) previous myocardial revascularisation - percutaneous coronary intervention (PCI), or coronary artery bypass graft (CABG).
  - For asymptomatic cardiovascular disease: patients with subclinical atherosclerosis diagnosed using imaging method such as i)vDoppler ultrasound, ii)vB-mode ultrasonography – measurement of carotid intima media thickness, iii)vintravascular ultrasonography, iv) Computed Tomography, v) Magnetic Resonance Imaging
8. ApoA-1  $\leq$  110 mg/dL
9. HDL-cholesterol  $\leq$  35 mg/dL or 0.9 mmol/L

